6.3 Duration of Subject Participation

Subjects enrolled in the trial will participate for approximately 24 months.

6.4 Withdrawal of Subjects

Each subject may voluntarily withdraw his/her participation from the study at any time. Investigators may discontinue a subject's participation in the study as deemed appropriate per safety measures and/or if the subject's medical condition contraindicates further study participation. All enrolled subjects will undergo the complete study follow-up for safety evaluation.

6.5 Loss to Follow-Up

A subject will be considered lost to follow-up and terminated from the study when all of the following criteria have been met:

- Documentation of three unsuccessful attempts on three different days over a period of three (3) months by the Investigator or his/her designee to contact the subject or next of kin, one of which should be by certified mail with signature confirmation
- Prior agreement of the Sponsor to remove the subject from the clinical investigation

6.6 Subject Confidentiality

All information concerning subjects or their participation in this trial will be considered confidential. Only authorized PQ Bypass personnel and designated consultants and regulatory agencies will have access to these confidential files. Enrolled subjects will be assigned a unique identifier that will be used to maintain confidentiality of each subject's medical information. Subject names and other protected health information will not be captured on the case report forms. In addition, angiographic and ultrasonic images submitted from the participating site to the Sponsor or angiographic reviewers for analysis should be redacted from all patient identifiers.

7.0 RISK-BENEFIT ASSESSMENT

7.1 Risks

There are standard risks associated with any interventional procedure or stent graft placement as well as risks specific to the PQ Bypass devices and procedure. Risks associated with any interventional procedure include access site hemorrhage or hematoma, access site pain, acute vessel closure, infection, renal insufficiency/failure due to excessive contrast load, and death. The risks stated below concern each system manufactured by PQ Bypass and their use in the PQ Bypass procedure.

Possible risks related to the PQ Bypass Guidewire Delivery System include, but are not limited to, the following: vessel dissection, perforation or wall trauma, embolism, infection, bruising or hemorrhage at the procedural access site, deep vein thrombosis, bleeding or infection.

Possible risks related to the PQ Bypass Stent Graft System include, but are not limited to, the following: thrombosis, stenosis or occlusion, aneurysm or pseudoaneurysm formation, vessel dissection, perforation or wall trauma, embolism, venous flow disruption (including deep vein thrombosis, edema or phlebitis), arteriovenous fistula formation, bleeding infection or side branch occlusion.

Additionally, subjects will be exposed to risks associated with conscious sedation, use of radiographic contrast and procedural medications. Subjects will be asked to take anti-platelet medication for this study, such as aspirin for life and Plavix

(clopidogrel) or Ticlid (ticlopidine) for length of follow-up. These medications have been approved to reduce the risk of cardiovascular events. An Investigator will discuss with each subject the standard risks associated with these medications.

Risk will be mitigated by working with Investigators who are experienced and skilled in endovascular techniques including use of re-entry tools and stent graft placement. Additionally, each Investigator will be thoroughly trained on proper device operation prior to device use. Risks will also be minimized in this study by adhering to the inclusion/exclusion criteria. For example, subjects with known allergies or contraindications to study medications (contrast, anti-platelet, heparin) will be excluded. Risks associated with device malfunctions or failures will be minimized through bench and in-vivo animal verification and validation testing prior to use in this study.

7.2 Benefits

Patients included in this study have lesions that are challenging to treat with conventional endovascular means. Based on previous treatments using commercially available devices and PQ Bypass's bench and animal testing, it is expected that the participants in this study will have their lesions successfully treated without the need for surgery. Bypassing lesions with the PQ Bypass Systems may allow physicians to treat challenging lesions in the femoral artery percutaneously, thereby avoiding the risks and morbidity of more invasive procedures such as surgical bypass or amputation.

8.0 STUDY PROCEDURE

8.1 Vascular Access and Guidewire Delivery

Investigators will access the target lesion and the corresponding ipsilateral vein using standard percutaneous techniques and devices. Patient eligibility will be confirmed prior to insertion of the study device, based on procedural imaging and sheath placement.

After eligibility confirmation, the Venous Locator (VL), Percutaneous Anastomotic Device (PAD) and Balloon Dilator (BD) will be used to deliver a guidewire from the arterial segment proximal to the target lesion, through the femoral vein and back into the reconstituted artery distal to the target lesion. This procedure is described in detail in the Guidewire Delivery System and Balloon Dilator IFUs (**Appendix II**). The number of deployment attempts for guidewire placement access at each anastomosis will be recorded.

8.2 Stent Graft Placement

Stent Grafts (SGs) of appropriate dimension are selected based on the instructions provided in the Stent Graft System IFU (**Appendix II**). SGs are then deployed in series, starting distally, until the bypass is complete. After placement, the Investigator uses a standard balloon dilation catheter to complete stent deployment, ensuring that the balloon is only inflated within the SGs' lumen.

8.3 Follow-Up

Subjects will return to the study center at 1 month (± 7 days), 3 months (± 14 days), 6 months (± 30 days), 12 months (± 45 days), 18 months (± 45 days) 24 months (± 60 days), 30 months (± 60 days) and 36 months (± 60 days) following the procedure for a follow-up evaluation. The subject will undergo lower-extremity arterial and venous duplex ultrasounds, venous health questionnaires and examined for any post-procedural complications or adverse events.

9.0 MATERIALS AND METHODS

Safety and performance evaluations will be conducted throughout the study. Such evaluations will be conducted on the case report forms.

9.1 Initial Eligibility

After subjects have signed an informed consent form and before the scheduled interventional procedure, subjects will undergo an initial eligibility evaluation. This evaluation may be conducted from an office visit within the previous 90 days. The evaluation will consist of the following:

- Pre-procedural CTA or MRA
- Pre-procedural venous ultrasound
- Review of inclusion/exclusion criteria

9.2 Baseline Evaluation

After subjects have signed an informed consent form and before the scheduled interventional procedure, subjects will undergo a baseline evaluation. This evaluation may be conducted from an office visit within the previous 30 days. The evaluation will consist of the following:

- Subject's demographic data (sex and date of birth)
- Medical history
- Rutherford score and Ankle-Brachial Index (ABI)
- Serum pregnancy test
- Venous Clinical Severity Score
- Villalta scale
- BUN and Creatinine
- Medication history and review

9.3 Procedural Evaluation

Final eligibility will be determined based on imaging study and sheath placement. Information on the lesion being treated and the specific vasculature used in its treatment will be collected. The procedural evaluation will consist of the following:

- Lesion length
- Lesion calcification (TASC II Classification)
- Lesion type
- Procedure time

- Access sites used
- Number of attempts to create each anastomosis
- Complications or adverse events

9.4 Discharge Evaluation

The discharge evaluation will consist of:

- Rutherford score and Ankle-Brachial Index (ABI)
- Arterial and Venous duplex-ultrasound assessment
- Complications or adverse events
- Concomitant medications

9.5 Follow-Up Evaluation

The evaluations at 1 month (± 7 days), 3 months (± 14 days), 6 months (± 30 days), 12 months (± 45 days), 18 months (± 45 days) 24 months (± 60 days), 30 months (± 60 days) and 36 months (± 60 days) post-procedure or when a subject withdraws prematurely from the study will consist of:

- Rutherford score and Ankle-Brachial Index (ABI)
- Venous Clinical Severity Score⁵⁸
- Villalta Scale⁵⁹
- Arterial and Venous duplex-ultrasound assessment
- Complications and adverse events
- Concomitant medications

10.0 INVESTIGATIONAL DEVICE DISTRIBUTION AND ACCOUNTABILITY

10.1 Device Accountability

The Investigator shall maintain adequate records of the receipt and disposition of all investigational devices. The Investigator is responsible for ensuring that the investigational devices are used only under the Investigator's supervision and are only used according to this protocol and any approved amendments. The Investigator will not supply an investigational device to any person not authorized to participate in the study. The Investigator shall document in CRFs the lot numbers of the devices used during a case. In addition, the Investigator shall keep complete and accurate records of all devices used or unused that have been returned to PQ Bypass in a Device Accountability Log provided by PQ Bypass.

10.2 Return of Devices

All unused investigational devices will be returned to the study Sponsor upon completion of the clinical study. All used investigational devices will be properly disposed of, per institutional procedures. Any investigational device that fails to perform correctly will be returned to the study Sponsor for analysis. The Investigator or his/her designated representative is responsible for device accountability and disposition of all used and unused devices. The study Sponsor

or its designated representative will conduct device reconciliation at the completion of subject enrollment or at the conclusion of the study.

11.0 ENDPOINTS AND STATISTICAL ANALYSIS PLAN

11.1 Endpoints Analyses and Reporting of Results

The study objective is to assess the safety and performance of the PQ Bypass System to access, deliver guidewires and implant stent grafts for a percutaneous fem-pop bypass.

The study is a feasibility study with no formal hypothesis testing and therefore no required sample size. Study results will be presented using descriptive statistics. Results from this study will be used to design additional clinical studies.

All subjects will be followed on an intent-to-treat basis. The device performance will be assessed based on a per-protocol analysis of the primary safety and effectiveness endpoints. An Intent-to-treat analysis, along with other secondary analyses, will also be completed and reported.

Demographic, baseline clinical and disease characteristics, procedural results and primary, secondary and all additional endpoints will be summarized using descriptive statistics.

All statistical analyses will be performed using SAS for Windows version 9.1 or higher.

Primary Safety Endpoint Reporting:

Safety assessment is achieved by recording and measuring Major Complication rates/Serious Adverse Event rates associated with the PQ Bypass procedure. The number and percentage 6-month MAE will be presented using descriptive Statistics. Using the Score approximation, the one-sided upper 95% confidence bound will be calculated and presented.

Primary Performance Endpoint Reporting:

Descriptive statistics of the primary performance endpoint which includes total number of patent PQB grafts, number and percentage of patent PQB grafts, and the one-sided 95% CI of the percentage using the Score approximation will be presented. The lower bound of the one-sided 95% CI will be compared to the performance goal of 70% (80% historical control rate – 10% Delta.)

Secondary Endpoint Analysis:

The secondary endpoint of primary assisted and secondary patency will be summarized using Kaplan-Meier survival analysis. Life tables will be created and a Kaplan-Meier survival curve will be presented.

The secondary endpoints of Procedural Success, Clinical Success and Technical

Success will be summarized by providing point estimates, number of subjects, and 95% confidence bounds calculated using the Score approximation.

Demographic, procedural and safety data:

Demographic and baseline clinical and disease characteristics will be summarized in tables. For continuous variables the summary will include number, mean, and standard deviation and 95% confidence intervals. Summaries for categorical variables will include the number and percent of subjects in each category.

Imputation for Missing Data

Imputations for missing data in (e.g. withdrawn subjects, loss to follow-up, missing data) will not be performed. Analyses will be performed with all available data only.

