6.2 Enrollment

Subjects will be considered enrolled into the study once informed consent has been signed and all eligibility criteria confirmed. Investigators will access the target artery and the corresponding ipsilateral vein using standard percutaneous techniques and devices. Patient eligibility will be confirmed prior to insertion of the study device, based on procedural angiogram and sheath placement.

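### The lead analysis of both primary endpoints, and on the natural reading of the 70% comparison, uses a per-protocol set that the available text does not define

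*Combined protocol and SAP*

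**What the plan says.** Section 11.1 gives the lead role to one population: "The device performance will be assessed based on a per-protocol analysis of the primary safety and effectiveness endpoints". ITT follows in second place: "An Intent-to-treat analysis, along with other secondary analyses, will also be completed and reported". I found no other mention of per-protocol. Section 15 defines a protocol deviation but does not grade deviations or link them to exclusion from analysis, and section 19 defines no analysis set.

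For the primary performance endpoint, section 11.1 will report the "total number of patent PQB grafts, number and percentage of patent PQB grafts" with a score confidence bound, and adds "The lower bound of the one-sided 95% CI will be compared to the performance goal of 70" percent. On missing data it says "Analyses will be performed with all available data only". The same section also states: "The study is a feasibility study with no formal hypothesis testing and therefore no required sample size". Section 11.2, however, writes null and alternative hypotheses against 70% and describes a non-inferiority aim.

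The nearest thing to an ITT denominator is in section 6.2: "Subjects will be considered enrolled into the study once informed consent has been signed and all eligibility criteria confirmed". Eligibility is confirmed there before the study device is inserted.

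**The concern.** A comparison with a fixed goal has no control arm in which a selection effect could partly cancel. If subjects who do badly are more likely to leave the analysed set, the patency percentage rises and nothing offsets it. The MAE bound can fall for the same reason.

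Failed delivery is one concrete route. The reported quantity is a count of patent grafts, and a subject in whom no graft was delivered may have none to count. A missing 6-month duplex is another. The available-data rule applies to every analysis, and the text does not say that a loss of patency seen on an earlier scan still counts when the 6-month scan is absent. Without a written definition, decisions on who is in the set could be made after outcomes are known. At stake are the headline patency rate and, if 70% is treated as a decision rule, whether the goal is reported as met.

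**Working it through.** **The plan's own figures.** Section 11.2 uses a true rate of 85%, one-sided alpha 0.05 and 80% power. With n = [(1.645√(p0(1−p0)) + 0.842√(p1(1−p1)))/(p1−p0)]² and p1 = 0.85:
- p0 = 0.70 gives 49.4, so 50.
- p0 = 0.75 gives 102.6, so 103.

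Both match the plan. Neither allows for per-protocol exclusions, and section 11.2 expects no loss to follow-up among the 100. Below I use 70%, the goal stated in section 11.1 and in the written hypotheses.

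**Passing rule.** The one-sided 95% score (Wilson) lower bound is

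L = [p + z²/2n − z√(p(1−p)/n + z²/4n²)] / (1 + z²/n), with z = 1.645.

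At n = 100, 78 patent gives L = 70.5% (meets) and 77 gives 69.4% (misses), so 78 are needed.

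**Worst-case example (every excluded subject is a failure).**
- 74/100: (0.7400 + 0.0135 − 0.0734)/1.0271 = 66.2%, misses.
- 74/95, after five failures are dropped: (0.7789 + 0.0142 − 0.0715)/1.0285 = 70.2%, meets.
- At the edge one failure is enough: 77/100 gives 69.4% and 77/99 gives 70.2%.

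**Chance of passing at a true 70%.** With no exclusion, P(X ≥ 78 | 100, 0.70) = 4.8%. The documents give no exclusion rate, so I assumed an overall rate e, with failures r times as likely to be excluded as successes. The success exclusion probability is s = e/(0.70 + 0.30r), and patency among those kept is q = 0.70(1−s)/(1−e). For e = 5% and r = 3: s = 0.05/1.6 = 0.03125 and q = 0.70 × 0.96875/0.95 = 71.4%. The passing probability is then summed over the binomial number of subjects kept.

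| Excluded | r = 1 (unrelated to outcome) | r = 2 | r = 3 |
|---|---|---|---|
| 3% | 4.6% | 5.7% | 6.5% |
| 5% | 4.7% | 6.7% | 8.2% |
| 10% | 4.8% | 9.7% | 14.3% |

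As an outer limit, dropping exactly 3, 5 or 10 failures gives 11%, 22% and 46%.

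**Chance that the two sets disagree on the goal.** With five failures dropped, the cut-off in the reduced set is 74/95. The sets then disagree when the full-set count is 74 to 77: 18% at a true 70%, 36% at 75%, 21% at 80% and 2% at 85%. With no exclusion, the goal is met 97.8% of the time at 85%.

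**Safety illustration.** Four MAEs in 100 subjects give an upper bound of 8.6%. If three subjects are excluded, the bound is 8.9%, 7.5%, 6.0% or 4.5% when 0, 1, 2 or 3 of them had an MAE.

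**The case against.** The best defence is that section 11.1 describes a feasibility study reported descriptively, with ITT results alongside, so any gap caused by per-protocol exclusions will be visible. Technical Success and Procedural Success would show failed deliveries. Duplex is scheduled at discharge, at 1, 3 and 6 months and on premature withdrawal (sections 8.3, 9.4 and 9.5). Section 6.4 adds: "All enrolled subjects will undergo the complete study follow-up for safety evaluation". Much of this stands and lowers the weight of the point. It does not supply a definition, however, and ITT reporting cannot reveal outcomes that are missing from both sets.

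Four stronger readings are tempting but not supported:
- *The 70% comparison has no analysis set.* The comparison sentence names none, but it follows the general statement that device performance is judged per protocol. Per-protocol is the natural reading.
- *The absence of a rule for conflicting per-protocol and ITT results is a defect in itself.* The section is descriptive and reports both, and the question disappears once one set governs.
- *The error rate is 11–46%.* Those figures require every excluded subject to be a failure. Nothing in the documents suggests that, and exclusion unrelated to outcome produces no inflation.
- *A safety conclusion could reverse.* There is no safety goal, so only the reported bound can move.

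The revision log also mentions an Appendix III justifying the primary endpoints, which is not in the text I had. The statement that per-protocol is undefined is limited accordingly.

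**Conclusion.** The point holds and should be fixed, at moderate weight. The lead set for both primary endpoints is undefined in the available text, in a design where outcome-related exclusion biases the estimate directly.

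The size depends on two assumptions: that 70% is read as the decision rule of section 11.2, and that exclusions run at 3–10% with failures two to three times as likely to be excluded. The chance of passing at a true 70% then goes from 4.8% to between 5.7% and 14.3%. A changed conclusion is realistic only near the goal. It is unlikely at the planned 85%, or if the 90% interim patency in section 2.4 (30 subjects, analysis set not stated) is sustained.

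**What to change.** 1. Make all enrolled subjects in whom study-device insertion was attempted the governing set for both primary endpoints and for the 70% comparison. State how this set relates to the enrolled population of section 6.2.
2. Count as patency failures all technical failures, and any documented loss of patency or clinically driven re-intervention before 6 months, even if the 6-month duplex is missing.
3. State how the governing analysis treats deaths before 6 months, and subjects with neither a 6-month duplex nor a documented failure.
4. Add a missing-equals-failure analysis for patency as a sensitivity analysis only. With missingness unrelated to outcome and a true 85%, the chance of reaching 78/100 falls from 97.8% to 80% with 5% missing (success rate 0.85 × 0.95) and to 41% with 10% missing (0.85 × 0.90).
5. Define the per-protocol set without reference to outcome and keep it as a sensitivity analysis.
6. Align the section 19 definition of primary patency, which omits the re-intervention clause, with section 5.2.

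The cost is SAP wording and a few extra tables, with no new data. The headline patency rate may be slightly lower.

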1.0 PRIMARY CONTACTS

Sponsor and Data Management	PQ Bypass, Inc. [name] [contact] [contact] [name] Vice- President Clinical and Regulatory Affairs PQ Bypass, Inc. [contact] Email: [contact]
Global Monitor / CRO Authorized EU Representative	[name] Quality Manager HealthLink Europe BV HealthLink International Inc. [name] The Netherlands Phone General: [name] [contact] E-mail: [contact] Web:www.healthlinkeurope.com
Legal Representative - Chile	Bioscience Consulting Inc. [name] [name] [contact] Email: [contact]
Core Lab	Vascular Ultrasound Core Lab [name] RN, RVT, FSVU, Technical Director [name] Business Office: [contact] [contact] [contact] [contact] http://vascore.org

PROTOCOL SUMMARY

Title:	PQ Bypass Systems for Femoropopliteal Bypass II (PQB 4 FP II)
Protocol Number	STP 115
Study Design:	Prospective, single-arm, multi-center, international, non-randomized, pre-market, safety and effectiveness clinical investigation evaluating the PQ Bypass Systems to access, deliver guidewires and implant stent grafts for a percutaneous femoropopliteal (fem-pop) bypass.
Study Objective:	To assess the safety and performance of the PQ Bypass System to access, deliver guidewires and implant stent grafts for a percutaneous fem-pop bypass.
Enrollment:	Up to 100 subjects will undergo a percutaneous fem-pop bypass, including up to 30 subjects in Germany.
Number of Sites	Up to 17 international sites (non U.S. sites).
Study Enrollment	24-month enrollment period: 
 • Initial enrollment: Q1, 2015 • Last enrollment: Q1, 2017
Study Duration	60 months (24-month enrollment and 36-month follow-up)
Primary Safety Endpoint:	Major Adverse Events (MAE) at 1 month. MAE is a composite endpoint defined as: 
 • Death • Target Vessel revascularization (TVR) • Target limb amputation

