Primary Performance Endpoint:	The rate of primary patency at 6 months defined as: no evidence of clinically significant stenosis ($\geq 50\%$) within the stent graft or immediately above or below the treated arterial segment based on duplex ultrasound (systolic velocity ratio of > 2.5), with no clinically-driven re-intervention within the stented segment. The primary performance endpoint will be assessed by an independent Core Lab.
Secondary Safety Endpoints:	
 • Major Adverse Events (MAE) through follow-up. • Major adverse vascular event (MAVE) through follow-up defined as stent thrombosis, target limb amputation, clinically apparent distal embolization, defined as causing end-organ damage (e.g. lower extremity ulceration, tissue necrosis, or gangrene), procedure related arterial rupture, acute limb ischemia or bleeding event requiring transfusion. • Major Blood Loss defined as transfusion of > 2 units packed red blood cells (PRBC) through discharge. • The combined rate of death of target vessel revascularization (TVR), index limb amputation, and an increase in Rutherford-Becker Classification by 2 classes (comparing pre- to post-procedural assessments) through follow-up. • Deep Vein Thrombosis (DVT) on ipsilateral limb defined as a symptomatic blood clot (thrombus) in the targeted deep vein (e.g. posterior tibial) through follow-up. • Venous Clinical Severity Score (VCSS) and Villalta Scale through follow-up. • Venous Assessment (Miller Scale) through follow-up. • Stent fracture identified via X-ray through follow-up. Optional per standard practice. Not applicable if Radiological Safety Committee approval is required (e.g. BFS Germany)
Secondary Performance Endpoints:	
 • Technical Success defined as successful delivery of the investigational devices to the identified area and removal of delivery system. • Procedural Success defined as successful delivery of the investigational devices to the

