5.2 Study Endpoints

Primary Safety Endpoint:

Major Adverse Clinical Events (MAE) at 1 month, defined as death, target vessel revascularization (TVR), target limb amputation.

Primary Performance Endpoint:

Primary Patency at 6 month, defined as no evidence of clinically significant stenosis ($\geq 50\%$) within the stent graft or immediately above or below the treated arterial segment based on duplex ultrasound (systolic velocity ratio of >2.5), with no clinically-driven re-intervention within the stented segment.

Secondary Safety Endpoints:

- Major Adverse Events (MAE) through follow-up.
- Major adverse vascular event (MAVE) through follow-up defined as stent thrombosis, target limb amputation, clinically apparent distal embolization, defined as causing end-organ damage (e.g. lower extremity ulceration, tissue necrosis, or gangrene), procedure related arterial rupture, acute limb ischemia or bleeding event requiring transfusion.
- Major Blood Loss defined as transfusion of >2 units packed red blood cells (PRBC) through discharge.
- The combined rate of death of target vessel revascularization (TVR), index limb amputation, and an increase in Rutherford-Becker Classification by 2 classes (comparing pre- to post-procedural assessments) through follow-up.
- Deep Vein Thrombosis (DVT) on ipsilateral limb defined as a symptomatic blood clot (thrombus) in the targeted deep vein (e.g. posterior tibial) through follow-up.
- VCSS and Villalta Scale through follow-up.
- Venous Assessment (Miller Scale) through follow-up.

- Stent fracture identified via X-ray through follow-up. (Optional per standard practice. Not applicable if radiological Safety Committee approval is required e.g. BFS Germany).

Secondary Performance Endpoints:

- Technical Success defined as successful delivery of the investigational devices to the identified area and removal of delivery system.
- Procedural Success defined as successful delivery of the investigational devices to the identified area and removal of delivery system in the absence of in-hospital MAEs.
- Clinical Success defined as Limb ischemia improvement by Rutherford-Becker (improvement in scale by ≥ 1) through follow-up.
- Limb ischemia by Rutherford-Becker Classification through follow-up.
- Primary Patency through follow-up.

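### The primary safety endpoint is defined as MAE at 1 month, but Section 11.1 specifies its rate and upper confidence bound for MAE at 6 months

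*Combined protocol and SAP*

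**What the plan says.** Two places define the primary safety endpoint, and they agree. The Protocol Summary gives "Major Adverse Events (MAE) at 1 month". Section 5.2 gives "Major Adverse Clinical Events (MAE) at 1 month, defined as death, target vessel revascularization (TVR), target limb amputation".

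The analysis is set out in Section 11.1, in the paragraph on reporting the primary safety endpoint: "The number and percentage 6-month MAE will be presented using descriptive Statistics". The next sentence reads "Using the Score approximation, the one-sided upper 95% confidence bound will be calculated and presented". It names no time point of its own.

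Two other statements bear on the point. Section 11.1 makes a general commitment that "primary, secondary and all additional endpoints will be summarized using descriptive statistics", which mentions neither a time point nor a bound. The secondary safety endpoints, in both the Protocol Summary and Section 5.2, include "Major Adverse Events (MAE) through follow-up".

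**The concern.** A primary endpoint and its specified analysis should name the same quantity. Here the definitions say 1 month and the analysis paragraph says 6 months. Someone who programs the primary safety table from Section 11.1 would produce a 6-month rate and bound. Someone who works from the endpoint definitions would produce a 1-month rate and would find no sentence that clearly attaches a bound to it.

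Safety has no hypothesis test, so the rate and its upper bound are the whole of the primary safety result. In an open, single-arm study, an unresolved conflict also leaves room to settle the time point after the data have been seen. A reader of the report could not tell which one had been prespecified.

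**Working it through.** **1. The passages side by side**

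| Place | Role | Time point for MAE |
|---|---|---|
| Protocol Summary, primary safety endpoint | definition | 1 month |
| Section 5.2, primary safety endpoint | definition | 1 month |
| Section 11.1, primary safety reporting, count and percentage | analysis | 6 months |
| Section 11.1, primary safety reporting, Score bound | analysis | none stated; follows directly on the 6-month sentence |
| Section 11.1, general descriptive sentence | analysis | none stated, no bound |
| Protocol Summary and Section 5.2, secondary safety | definition | through follow-up |

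All of these are current text, so this is not a difference between the amendment log and the body. The log entry for revision E records that the primary safety endpoint was updated, so the 6-month wording may be a leftover. That is an inference, and the finding does not need it. Six months is the time point of the other primary endpoint: "Primary Patency at 6 month, defined as no evidence of clinically significant stenosis".

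**2. Does any stated figure depend on the MAE time point?**

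The documents give no MAE rate, safety goal, safety power or safety bound, so there is no safety figure to reproduce. The only sample size calculation (Section 11.2) is for patency. It reproduces with the one-sample score formula

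n = [(z₀.₉₅·√(p₀(1−p₀)) + z₀.₈₀·√(p₁(1−p₁))) / (p₁−p₀)]², with p₁ = 0.85, one-sided alpha 0.05 and power 80%:

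- p₀ = 0.70: n = 49.4, rounded up to 50, as stated.
- p₀ = 0.75: n = 102.57, rounded up to 103, as stated.

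MAE does not enter this calculation. Changing its time point alters no sample size or power.

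**3. How far the reported bound could move**

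Inputs: N = 100 (Section 11.2); one-sided 95% Score (Wilson) upper bound, z = 1.645 (Section 11.1). Event counts are assumed. With p = x/N,

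upper = [p + z²/(2N) + z·√(p(1−p)/N + z²/(4N²))] / (1 + z²/N).

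For x = 5: z²/(2N) = 0.01353; the square root is √(0.000475 + 0.0000676) = 0.02329; the numerator is 0.05 + 0.01353 + 1.645 × 0.02329 = 0.1018; dividing by 1.02706 gives 0.0992.

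| Assumed events of 100 | Rate | Upper bound |
|---|---|---|
| 0 | 0% | 2.63% |
| 2 | 2% | 5.86% |
| 5 | 5% | 9.92% |
| 10 | 10% | 16.04% |
| 20 | 20% | 27.33% |

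On a fixed denominator, cumulative MAE at 6 months cannot be below MAE at 1 month, so the 6-month bound is equal or higher:

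- no events between 1 and 6 months: no difference;
- 2 events by 1 month and 5 by 6 months: 5.9% against 9.9%, about 4 percentage points;
- 5 events by 1 month and 10 by 6 months: 9.9% against 16.0%, about 6 percentage points.

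These pairs are illustrations, not predictions. Section 11.1 also provides for a per-protocol analysis on available data without imputation, so the denominators may be below 100 and may differ between the two time points.

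**The case against.** The strongest reply is that nothing inferential turns on this. Section 11.1 calls the study a feasibility study without formal hypothesis testing, and only patency has a performance goal. Both MAE rates are in effect planned: the general descriptive sentence covers the 1-month endpoint, the secondary endpoint covers later MAE, and visits at 1 and 6 months are both scheduled. The bound sentence carries no time point and sits under the primary safety heading, so it can be read as applying to the endpoint as defined. With two definitions agreeing on 1 month, a careful analyst might query the mismatch or follow the definitions. The revision log also mentions an Appendix III justifying the endpoints, which is not in the text available here and might show the intent.

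Much of this stands. No decision rule is affected, no data would go uncollected, and the 1-month bound can be computed from a reported count and denominator. The size shown above depends wholly on assumed counts.

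It does not remove the conflict. The general sentence gives no time point and no bound, so it does not override specific text under the primary safety heading. The natural antecedent of the bound sentence is the 6-month rate just before it. Reading it otherwise means setting aside the only time point that the paragraph contains. An appendix could explain which time point was meant, but the three passages would still disagree.

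**Conclusion.** The concern holds. The Protocol Summary and Section 5.2 define primary safety as MAE at 1 month, and the paragraph that specifies its analysis names 6 months. No sentence specifies a Score bound for 1-month MAE.

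The effect is limited to which rate and bound are reported as the primary safety result. Alpha, power, sample size and the patency comparison are untouched. The numerical effect is unknown because the documents give no MAE rate. Under the assumed counts, at N = 100 and on a fixed denominator, it runs from nil to about 6 percentage points on the upper bound.

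It must be corrected because it concerns one of the study's two primary endpoints. That is the only ground for the priority.

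**What to change.** In Section 11.1, under primary safety reporting, replace the 6-month time point with MAE at 1 month, so that it matches the Protocol Summary and Section 5.2. Attach the one-sided upper 95% Score bound explicitly to that 1-month rate. Report 6-month MAE under the existing secondary endpoint of MAE through follow-up, labelled as secondary.

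If the sponsor did intend 6 months, amend the Protocol Summary and Section 5.2 instead. Either way, all three places should give one time point.

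The cost is a one-line text correction. Visits at 1 and 6 months are already scheduled, so there is no added data collection and no burden on subjects.
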